**9.3. Exclusion Criteria**

Subjects who meet any one of the following criteria (Table 9.3-1) will be excluded from this clinical investigation.

	
 
1. Subject who is taking (or is planning to take) chronic or lifelong anticoagulation within 15 months following index procedure.
 
2. Subject with an indication for the index procedure of acute ST elevation MI (STEMI)
 
3. Subject with an indication for the index procedure of Non ST elevation MI (NSTEMI), based on the 3rd Universal MI definition (1)
 
4. Subject with treatment with another coronary stent, other than SYNERGY, during the index procedure
 
5. Subject with planned staged procedures. (Note: Planned staged procedures are allowed if performed within 7 days and with only SYNERGY stents).
 
6. Subject has a known allergy to contrast (that cannot be adequately pre-medicated), the SYNERGY stent system or protocol-required concomitant medications (e.g., everolimus or structurally related compounds, polymer or individual components, all P2Y12 inhibitors and aspirin)
 
7. Subject with implantation of a drug-eluting stent within 9 months prior to index procedure
 
8. Subject previously treated at any time with intravascular brachytherapy
 
9. Subject has an active peptic ulcer or active gastrointestinal (GI) bleeding
 
10. Subject is participating in an investigational drug or device clinical trial that has not reached its primary endpoint (Note: registry, observational, data collection studies are not exclusionary)
 
11. Subject intends to participate in an investigational drug or device clinical trial within 15 months following the index procedure (Note: registry, observational, data collection studies are not exclusionary)
 

--	---

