**Table 9.3-1: Exclusion Criteria**

Exclusion Criteria
	
 
12. Subject judged inappropriate for discontinuation from P2Y12 inhibitor use at 3 months, due to another condition requiring chronic P2Y12 inhibitor use
 
13. Subject with planned surgery or procedure necessitating discontinuation of P2Y12 inhibitor within 3 months following index procedure
 
14. Subject is a woman who is pregnant or nursing
 
15. Subject with a current medical condition with a life expectancy of less than 15 months
 
16. Target lesion(s) is located in the left main
 
17. Target lesion(s) is located within 3 mm of the origin of the left anterior descending (LAD) coronary artery or left circumflex (LCx) coronary artery by visual estimate
 
18. Subject has unprotected left main coronary artery disease (> 50% diameter stenosis)
 
19. Planned treatment of more than 3 lesions
 
20. Planned treatment of lesions in more than 2 major epicardial vessels
 
21. Target lesion(s) treated that involves complex bifurcation (i.e. bifurcation lesion treated with more than one stent)
 
22. Target lesion(s) is restenotic from a previous stent implantation
 
23. Target lesion(s) is located within a saphenous vein graft or an arterial graft
 
24. Target lesion(s) with a TIMI flow 0 (total occlusion) or TIMI flow 1 prior to guide wire crossing
 
25. Thrombus, or possible thrombus, present in the target vessel (by visual estimate)
 

----------------------------------	---

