### 12.2.1. Analysis Sets

For the EVOLVE Short DAPT Study, a subject is considered enrolled once an informed consent form has been signed and the subject has received at least one commercial SYNERGY stent. Enrolled subjects must meet all inclusion and no exclusion criteria. The analysis set for the test group includes enrolled subjects who meet criteria for discontinuation of P2Y12 inhibitor and who discontinue P2Y12 inhibitor at 3 months. The analysis set will be used as the test group in the propensity score model.

For the death/MI co-primary endpoint analysis, the EVOLVE Short DAPT-like high risk for bleeding subjects will be extracted from HCRI DAPT, PE+ PAS, and PE PROVE studies to form the historical control group. For the secondary bleeding endpoint analysis, the EVOLVE Short DAPT-like high risk for bleeding subjects will be extracted from HCRI DAPT study only to form the historical control group. Bleeding events were not adjudicated by the CEC in the PE+PAS or the PE-PROVE study.

The EVOLVE Short DAPT-like subjects are defined as subjects who meet the EVOLVE Short DAPT Study inclusion criteria and do not meet any of the following exclusion criteria at the time of the index procedure:

- indication for the index procedure of acute ST elevation MI (STEMI) or Non ST elevation MI (NSTEMI),
- previously treated with intravascular brachytherapy,
- left main target lesion,

- more than 3 lesions treated,
- more than 2 vessels treated,
- bifurcations,
- in-stent restenosis,
- saphenous vein graft,
- TIMI flow 0 (total occlusion) or TIMI flow 1 prior to guide wire crossing, and
- thrombus or possible thrombus present in the target vessel (by visual estimate).

The high risk for bleeding subject set is defined as a set of subjects who meets one or more of the following criteria at the time of enrollment:  $\geq 75$  years of age and, in the opinion of the investigator, the risk of bleeding associated with  $>3$  months of DAPT outweighs the benefit, chronic or lifelong anticoagulation therapy, history of major bleeding (severe/life threatening or moderate bleeding based on the GUSTO classification) within 12 months of the index procedure, stroke (ischemic and hemorrhagic), or renal insufficiency (creatinine  $\geq 2.0$  mg/dl) or failure (dialysis dependent), and platelet count  $\leq 100,000$   $\mu\text{L}$ .

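### Historical controls are screened on ten bullets while test subjects must pass all 25 exclusions, which may inflate the control death/MI rate toward non-inferiority by an amount the documents cannot settle

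*Combined protocol and SAP*

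**What the plan says.** For the test group, section 12.2.1 states: "Enrolled subjects must meet all inclusion and no exclusion criteria". Section 9.3 and Table 9.3-1 number 25 exclusions.

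For the controls, the same section defines an EVOLVE Short DAPT-like subject as one who satisfies the inclusion criteria and who "do not meet any of the following exclusion criteria at the time of the index procedure". Ten bullets follow. The section does not say why the list is shorter, or whether the source studies (HCRI DAPT, PE+ PAS, PE PROVE) already applied the remaining exclusions.

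Exclusions that bind the test group but are absent from the control list include:

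- Exclusion 7: "Subject with implantation of a drug-eluting stent within 9 months prior to index procedure".
- Exclusion 15: "Subject with a current medical condition with a life expectancy of less than 15 months".
- Exclusion 17: "Target lesion(s) is located within 3 mm of the origin of the left anterior descending (LAD) coronary artery" (or of the circumflex).
- Exclusion 18: "Subject has unprotected left main coronary artery disease" above 50% stenosis. The control list bars only a left main target lesion.

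Section 12.1.1.3 adjusts the comparison by propensity score quintiles on the covariates in Table 12.1-1. Section 12.2.2 says sensitivity analyses may be conducted, and names none for this difference.

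**The concern.** The death/MI co-primary endpoint is a non-randomised comparison, so it depends on the two groups having passed the same screen. An exclusion that removes higher-risk patients from the test side only leaves such patients free to remain among the controls. If they do remain, the control rate rises and a worse test result can fall inside the margin.

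Life expectancy is the plainest case. The endpoint counts all deaths between 3 and 15 months, and exclusion 15 removes test subjects expected to die within 15 months. No matching screen is written for controls.

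The covariates do not obviously repair this. Table 12.1-1 has history of PCI but not its timing, and CASS site but not distance from the ostium. It has nothing on untreated left main disease or on life expectancy.

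The stent thrombosis co-primary is not at stake, because it is tested against a performance goal without these controls.

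**Working it through.** **1. Line-by-line match.** The ten control bullets correspond to exclusions 2 and 3 (one bullet), 8, 16, 19, 20, 21, 22, 23 (saphenous vein graft only), 24 and 25. That is 11 of 25, so 25 − 11 = 14 are not applied: 1, 4, 5, 6, 7, 9, 10, 11, 12, 13, 14, 15, 17 and 18. The arterial-graft part of 23 is also missing.

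Not all 14 matter:

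- Allergy (6), other trials (10, 11) and pregnancy (14) are unlikely to move death/MI.
- Exclusions 4 and 5 are tied to SYNERGY.
- Exclusion 1 came in with the April 2017 revision. Some test subjects were enrolled on anticoagulation before it, and anticoagulant therapy is a covariate.
- Exclusions 7, 15, 17 and 18 are the substantive ones for death/MI.

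**2. The plan's own figures (section 12.1.1.2).** Inputs: 5.6% in both groups, margin 2.52 points, one-sided 0.025, power 85%.

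n = (1.960 + 1.036)² × 2 × 0.056 × 0.944 / 0.0252² ≈ 1,495 per group, against 1,500 stated. Then 1,500 × 1.1 = 1,650, and 1,650 / (0.85 × 0.97) = 2,001, against 2,000 stated. The planned size reproduces.

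**3. Standard error at the null.** True rates 5.6 + 2.52 = 8.12% (test) and 5.6% (control), with 1,650 and 1,643 subjects:

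SE = √(0.0812 × 0.9188/1,650 + 0.056 × 0.944/1,643) = 0.00880, or 0.880 points.

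**4. Effect of a residual control excess.** Let f be the share of controls who would fail an omitted exclusion and y their death/MI rate. The documents give neither, so both are assumed. The eligible controls are taken to run at 5.6%, and no part of the excess is removed by adjustment.

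Shift d = f × (y − 5.6). One-sided error = Φ(−1.96 + d/0.880).

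| f (assumed) | y (assumed) | d, points | d / 2.52 | One-sided error |
|---|---|---|---|---|
| 0 | – | 0 | 0 | 2.5% |
| 3% | 12% | 0.03 × 6.4 = 0.19 | 8% | 4.1% |
| 5% | 15% | 0.05 × 9.4 = 0.47 | 19% | 7.7% |
| 10% | 15% | 0.10 × 9.4 = 0.94 | 37% | 18.6% |

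In relative terms, f = 5% at twice the risk gives d = 0.05 × 5.6 = 0.28 points and an error of 5.0%. If the extra controls were at lower risk (f = 10%, relative risk 0.7), d = −0.17 points and the error falls to 1.6%. The sign depends on the inputs.

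**5. Plausibility of the inputs.** The synopsis footnote to the 5.6% gives 11/85 (12.9%) for PE PROVE, against 13/253 (5.1%) and 14/318 (4.4%) for the other two sources. A subset of 85 is about 5% of 1,643. This shows that a subgroup of that size and event rate exists in the control data. It does not show that the omitted exclusions produced it.

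**The case against.** A reader might infer that the control rate is in fact inflated. The documents do not support that, for four reasons.

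- The source studies' full eligibility rules are not given, and a source may already bar patients whom the control list does not. One such case is documented: section 12.2.2 says HCRI DAPT, which supplies 1,240 of the 1,643 controls, did not enrol subjects expected still to be on an anticoagulant at randomisation. Whether any control has, for example, unprotected left main disease is unknown.
- The control list excludes bifurcations without qualification, while exclusion 21 removes only those treated with more than one stent. If bifurcations carry higher risk, this lowers the control rate and works the other way.
- The planned test adjusts for age, heart failure, prior MI, PCI and CABG, ejection fraction, renal disease, CASS site and more. These are partial proxies and may absorb some of any excess.
- The models are built by a team blinded to outcome. That prevents selection on results, but it does not align the two screens.

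A reader might also carry the argument to bleeding. For active ulcer or GI bleeding (exclusion 9) it is possible but weak: all bleeding controls come from HCRI DAPT, which the Introduction says mainly excluded patients at high bleeding risk. For exclusion 13, "Subject with planned surgery or procedure necessitating discontinuation of P2Y12 inhibitor within 3 months following index procedure", it does not hold, because bleeding from such surgery would largely precede the 3 to 15 month window. For exclusion 12 (another condition requiring a chronic P2Y12 inhibitor) the documents support no direction of risk on any endpoint.

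What stands is the unequal rule itself, unexplained, with four plausibly prognostic exclusions outside both the control screen and the covariate list.

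**Conclusion.** The asymmetry is explicit in the current text: 14 of 25 exclusions, plus the arterial-graft part of 23, are not applied to controls. It may bias the death/MI comparison toward non-inferiority. The actual size and net sign are unknown.

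The errors of 4.1%, 7.7% and 18.6% are unadjusted illustrations. They rest on assumed shares of 3% to 10%, assumed event rates of 12% to 15%, and full survival of the excess through quintile adjustment. They should not be read as estimates for the planned analysis. They show that a modest residual excess matters: 0.28 points, about a ninth of the margin, would double the one-sided error. That, and the low cost of repair, makes the change worth asking for.

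**What to change.** In section 12.2.1, before the outcome-blinded team fits either propensity model:

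1. For each of the 14 exclusions and the arterial-graft part of 23, state whether each source study already applied it and whether its database records it. Apply to controls every one that was not already applied and is recorded. Treat exclusion 1 explicitly, since part of the test group was enrolled before it existed.
2. Align the control bifurcation rule with exclusion 21.
3. List the exclusions that cannot be applied. Those that rest on prospective judgement, such as life expectancy, may be among them.
4. For those, pre-specify a tipping-point analysis reporting the downward shift in the control death/MI rate at which non-inferiority is lost. For scale, on unadjusted figures with 5.6% observed in both groups, a shift of 1.0 point leaves SE = √(0.056 × 0.944/1,650 + 0.046 × 0.954/1,643) = 0.767 points and an upper bound of 1.00 + 1.96 × 0.767 = 2.50, just inside 2.52.
5. Restate the available control counts, now given as about 1,643 for death/MI and 1,240 for bleeding.

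The cost is one re-extraction, revised wording, somewhat fewer controls and slightly less power.

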### **12.2.2. Control of Systematic Error/Bias**

An independent Clinical Events Committee (CEC) will review clinical events encountered during the study. The CEC will be blinded to the study center and subject identification to the extent possible.

Handling of dropouts and missing data will depend on their frequency and the nature of the outcome measure. The distribution of prognostic factors between subjects with and without data will be examined. Adjustments for missing data will be performed if deemed necessary to eliminate or minimize bias and will be described completely. Statistical models that account for censored data will be employed in appropriate circumstances, e.g., for time-to-event outcomes. Sensitivity analyses may be conducted to assess the impact of different assumptions on interpretation of the results. Outlier values will be evaluated and values determined to be invalid will be queried. All data will be included in the analysis.

#### Propensity Scores Modeling Approach

To avoid potential bias, an independent propensity score model team, who is blinded to the outcome data, will develop two propensity score models based on the same set of covariates with three historical studies used in the first model and one historical study used in the second model.

The first propensity score model for the death/MI co-primary endpoint will be based on the analysis set for the test group from the EVOLVE Short DAPT Study and the EVOLVE Short DAPT-like high risk for bleeding subjects for the control group from HCRI DAPT, PE+ PAS, and PE PROVE studies.

The second propensity score model for bleeding will be based on the analysis set for the test group from the EVOLVE Short DAPT Study and the EVOLVE Short DAPT-like high risk for bleeding subjects for the control group from HCRI DAPT study. Subjects who were on long-term anticoagulation therapy and who were anticipated to still be on an anticoagulant at the time of randomization were not eligible for enrollment in HCRI DAPT study. In order to make a like-

to-like comparison between test and control groups, subjects with a need for chronic or lifelong anticoagulation therapy in the test group will be excluded from the second propensity score model for the bleeding secondary endpoint.

The independent propensity score model team will select the appropriate propensity score models prior to the endpoint analyses and file the propensity score baseline covariate modeling as an IDE supplement. The selected propensity score models will be delivered to an independent outcome reporting team for the endpoint analyses. The independent outcome reporting team will use these propensity score models to test the hypotheses of the test group compared to the control group and to compare other clinical outcomes between the test group and control group.

The missing data for the propensity score model covariates will be imputed. The within-study median value of the non-missing covariate for the subjects used in the propensity score model will be used as the imputed value for the missing continuous covariate. The within-study mode value of the non-missing covariate for the subjects used in the propensity score model will be used as the imputed value for the missing discrete covariate.

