### 7.2. Secondary Endpoint

- Rate of bleeding, based upon the Bleeding Academic Research Consortium (BARC) classification (types 2, 3 and 5) (59), between 3 and 15 months in subjects not taking chronic anticoagulation.

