### 12.1.2. Secondary Endpoint

The rate of bleeding, based upon the Bleeding Academic Research Consortium (BARC) classification (types 2, 3 and 5), between 3 and 15 month expressed as the proportion of subjects who experience bleeding between 3 and 15 months among all subjects who either experience bleeding between 3 and 15 months or survive free of bleeding for at least 425 days (analysis excludes subjects on chronic anticoagulants).

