#### 12.1.2.1. Hypothesis

The null hypothesis that the difference of bleeding rates between test group and historical control group is greater than or equal to zero will be tested against the alternative hypothesis that the difference between test group and historical control group is less than zero:

$$H_0: P_{MB-3M} - P_{MB-12M} \geq 0$$

$$H_1: P_{MB-3M} - P_{MB-12M} < 0$$

where  $P_{MB-3M}$  and  $P_{MB-12M}$  are the 3 to 15-month bleeding rates for the 3-month DAPT test group and the 12-month DAPT historical control group, respectively.

The historical control group for the hypothesis testing for bleeding is only from HCRI DAPT Study minus TAXUS. A second propensity score model will be developed based on the same set of covariates used in the propensity score model for the death/MI co-primary endpoint. The second propensity score model using quintile adjustment for the bleeding will be used to test the one-sided hypothesis of superiority of the test group compared to historical control group.

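### For the bleeding comparison, the chronic anticoagulation exclusion is written for the test group only, and the source-study rule relied on for the controls is narrower

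*Combined protocol and SAP*

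**What the plan says.** Sections 7.2 and 12.1.2 define the secondary endpoint for people not on chronic anticoagulation, without naming a group: "between 3 and 15 months in subjects not taking chronic anticoagulation" and "analysis excludes subjects on chronic anticoagulants". The synopsis hypothesis places the same restriction beside the test group.

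Section 12.1.2.1 fixes the comparator: "The historical control group for the hypothesis testing for bleeding is only from HCRI DAPT Study minus TAXUS". The second propensity model is "based on the same set of covariates used in the propensity score model for the death/MI co-primary endpoint", and Table 12.1-1 includes anticoagulant therapy among those covariates.

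Section 12.2.2 (Propensity Scores Modeling Approach) puts the restriction into practice. It first notes that long-term anticoagulant users "who were anticipated to still be on an anticoagulant at the time of randomization were not eligible for enrollment in HCRI DAPT study". It then concludes, for the sake of a like-to-like comparison, that "subjects with a need for chronic or lifelong anticoagulation therapy in the test group will be excluded from the second propensity score model".

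Section 12.2.1 says how controls are extracted. They must meet the trial's inclusion criteria, avoid a listed subset of its exclusions, and be at high risk for bleeding. The listed subset does not contain anticoagulation. The high-risk definition still contains "chronic or lifelong anticoagulation therapy, history of major bleeding". In the current eligibility tables, anticoagulation has gone from inclusion criterion 1 (section 9.2) and is now exclusion criterion 1 (section 9.3): "Subject who is taking (or is planning to take) chronic or lifelong anticoagulation within 15 months following index procedure".

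**The concern.** The two groups are cleared of chronic anticoagulation by different rules. Test subjects are removed for a chronic or lifelong need. Controls are cleared only by another study's enrolment rule, which has two conditions: long-term use, and an expectation of still being treated at randomization. A long-term user expected to stop before randomization meets the first condition but not the second, and so was not barred. The rule also concerns expected use, not actual use.

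No sentence in the extraction rules closes this gap. If such controls exist, their background anticoagulation adds bleeding to the control rate only for the part of the 3 to 15 month window in which they were treated. Some of an observed reduction would then reflect anticoagulation and not shorter DAPT. The endpoint is tested for superiority, so the bias runs toward the claim.

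**Working it through.** **1. The plan's own figure.** Inputs from section 12.1.2.2 and the synopsis: control rate 4%, test rate 2.19%, 1,240 controls, 1,650 test subjects, one-sided 0.025.

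- Pooled rate = (0.04 × 1,240 + 0.0219 × 1,650) / 2,890 = 0.02967
- Null SE = √[0.02967 × 0.97033 × (1/1,240 + 1/1,650)] = 0.00638
- Alternative SE = √[0.04 × 0.96/1,240 + 0.0219 × 0.9781/1,650] = 0.00663
- Power = Φ[(0.0181 − 1.96 × 0.00638) / 0.00663] = Φ(0.845) = 80.1%

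This reproduces the stated 80%.

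**2. Effect of unscreened controls, unadjusted.** Let h be the share of the 1,240 controls on chronic anticoagulation and RR their bleeding rate relative to other controls. The documents give neither, so both are assumed. Suppose no true difference, with 4% bleeding in everyone else.

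- Control rate = 4% × [1 + h(RR − 1)]
- Bias b = 4% × h(RR − 1)
- SE = √[pc(1 − pc)/1,240 + 0.04 × 0.96/1,650], with pc the control rate
- One-sided error = Φ(b/SE − 1.96)

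Example, h = 5%, RR = 3: pc = 4.4%, b = 0.40 points, SE = 0.756 points, error = Φ(0.529 − 1.96) = 7.6%.

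| h | Controls affected | Bias in points (RR 2 to 3) | One-sided error (RR 2 to 3) |
|---|---|---|---|
| 0 | 0 | 0 | 2.5% |
| 1% | 12 | 0.04 to 0.08 | 2.8% to 3.2% |
| 2% | 25 | 0.08 to 0.16 | 3.2% to 4.05% |
| 5% | 62 | 0.20 to 0.40 | 4.5% to 7.6% |

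The planned difference is 4% − 2.19% = 1.81 points.

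**3. What quintile adjustment does.** Section 12.1.1.3 averages five quintile differences with equal weight. Suppose all affected controls fall in the lowest-score quintile, which holds n controls. The adjusted bias is then 4% × (RR − 1) × h × 1,240 / (5n). A quintile has 2,890/5 = 578 subjects; n is assumed to be 300 to 500. At h = 5%, RR = 2:

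- n = 300: 4% × 62/300 / 5 = 0.165 points
- n = 500: 4% × 62/500 / 5 = 0.099 points

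The crude bias is 0.20 points, so adjustment reduces it without removing it. A simulation of the planned estimator agrees (6,000 runs per cell, RR = 3, one covariate separated by 0.3 or 0.6 SD, affected controls given a score near zero). One-sided error was 3.1% to 3.6% at h = 2% and 4.6% to 5.7% at h = 5%, against 4.05% and 7.6% unadjusted.

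**4. Power after excluding the same subjects from the controls.** Step 1 repeated with fewer controls:

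| Controls removed | Controls left | Power |
|---|---|---|
| 0% | 1,240 | 80.1% |
| 2% | 1,215 | 79.7% |
| 5% | 1,178 | 79.1% |
| 10% | 1,116 | 78.0% |

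**The case against.** The strongest reply is that the control group was screened at source. The sentence before the test-only exclusion gives that reason, and the revision history describes anticoagulated subjects as not represented in the control study. Someone with a lifelong need would ordinarily be expected still to be treated at randomization. This stands for most chronic users and is why the share may be near zero. It does not cover long-term users expected to stop.

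Second, the wording in section 12.1.2 names no group and could be read as already removing such controls. That is a fair reading, but the operative instruction in section 12.2.2 says something narrower, so the two need reconciling.

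Third, a reader might infer that section 12.2.1 actively brings anticoagulated patients into the comparator. The documents do not support that. Controls must also meet the inclusion criteria, and criterion 1 no longer lists anticoagulation. Under the current text, the leftover clause cannot qualify a control alone; the defect is that a control who qualifies on another criterion is not removed.

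Fourth, the exposure of such controls is unknown. The documents do not state when HCRI DAPT randomized; a time near 12 months can only be guessed from a cited title. Test subjects on time-limited anticoagulation may also remain, so complete separation on the covariate is not certain.

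Fifth, the propensity team works blinded to outcomes, and adjusted baseline variables are to be compared, so an imbalance might be seen. That helps detection but sets no rule for action. Finally, bleeding is not part of the study success criteria, which limits the consequence.

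**Conclusion.** The narrow point holds. One restriction, defined for the endpoint as a whole, is carried out by an explicit exclusion in one group and by a narrower, expectation-based rule in the other, and section 12.2.1 conflicts with sections 9.2, 9.3 and 12.1.2. Bias from any remaining chronically anticoagulated controls would favour superiority, and the propensity adjustment would remove it only in part.

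The size cannot be determined from the documents. A reader might infer from the table that type I error is inflated by a known amount. It is not known: every figure above 2.5% rests on assumed values of h and RR, with RR applied over the whole window, and the effect is negligible if h is near zero. Nor is it right that adjustment does nothing, since the planned estimator lowers the error in the cases examined. This is a cheap improvement to a secondary analysis and does not show that the comparison is invalid.

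**What to change.** - **Section 12.2.2:** exclude subjects with chronic or lifelong anticoagulation at the index procedure from both groups in the second propensity model, under one stated definition. Keep the chronic or lifelong criterion. Substituting any recorded anticoagulant use would change the endpoint population.
- **Section 12.2.1:** state that the anticoagulation clause does not qualify a control for the bleeding comparison, and add chronic or lifelong anticoagulation to the exclusions for that comparison.
- **Reporting:** give the number of controls removed.
- **Covariates:** keep anticoagulant therapy in the second model unless it is constant after the exclusion.

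The cost is wording and a few controls, about 12 for each 1% of 1,240. Section 12.1.1.3 states that the covariates are available in the historical studies, so no new data collection should be needed, provided the recorded field can identify chronic use. Power falls by 1.0 point if 5% of controls are removed and by 2.1 points if 10% are.
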